6.1.2 Ketamine Arm

Patients will receive up to six treatments over three to five weeks. Ideally patients will receive treatments at regular intervals of two times per week for three weeks. The window allows for modifications based on clinician discretion and patient schedules.

Confidential Page **17** of **40** Protocol V7.0 16Feb2022

Ketamine will be administered according to the standard dose of 0.5mg/kg infusion over a 40 min period. The investigator will be able to modify the dose if clinically warranted. Treatments will be given two times a week for a maximum of six treatments after which the acute arm of the study will be complete.

Patients will be clinically assessed prior to each treatment to evaluate response and appropriateness for continued treatment. Patients will be assessed for any adverse events and treated per investigator discretion.

Patients will receive both patient rated and clinician rated behavioral scales at all treatment visits (Baseline/Visit 1, Visit 2, Visit 3, Visit 4, Visit 5, Visit 6, and EOT Visit).

6.2 Assessment for Response during Acute Treatment Phase

6.2.1 Responders

Patients who have a decrease of \geq 50% on the QIDS-SR-16 from Baseline/Visit 1 to the EOT Visit will be classified as a responder. These patients may be included in the six month follow-up phase, depending on the date of enrollment relative to the end of study. The clinician may decide to stop treatment before the maximum number of visits and schedule the patient for an EOT Visit.

6.2.2 Non-Responders

Patients who have less than a 50% decrease in QIDS-SR-16 score from the Baseline/Visit 1 to the EOT Visit will be classified as non-responders. These patients will not be seen for follow-up visits. However, these patients will receive a follow-up phone call one month after the End of Treatment Visit to ask about AEs/SAEs, treatment with ECT, ketamine, psychotropic medications, and complete the PGI-S and PGI-I, QIDS and MADRS assessments. Patients will be referred to their clinical provider for ongoing treatment of depression. Continuity of care between study staff and clinical providers will be carefully managed in order to provide optimal ongoing psychiatric care for the patient.

6.3 Concomitant Medication

6.3.1 Medications Allowed During Study

Patients will be allowed to continue their existing psychotropic medications. Changes in psychotropic medications throughout the trial are best avoided but are permitted according to investigator discretion. These medications must be recorded on the Psychiatric Medication Log.

Subjects should continue medications for other conditions and be reminded to tell study staff of any changes to medical history or concomitant medications. This will be assessed at each visit prior to treatment. All subjects should receive optimal care for any side effects occurring during the study (nausea, headache, etc.) according to local

Confidential Page **18** of **40** Protocol V7.0 16Feb2022

standards of care or evidence based guidelines, and at the discretion of the investigator.

6.3.2 Prohibited Medications

Patients should not be enrolled in the study if they are taking any medication that is contraindicated for ECT or ketamine treatment.

Changes in medical history and concomitant medications will be assessed at each visit and patients may be withdrawn from the study at any point if they are taking prohibited medication.

7. Study Procedures

7.1 Screening Period (Maximum of 28 days)

- Informed Consent: An investigator and/or other delegated study team member will discuss all risks and benefits of participation and review the study visit schedule with the patient. The patient will sign the informed consent form prior to any study procedures being performed.
- Assessment of Inclusion/Exclusion Criteria
- Demographics
- Medical History, including psychiatric history and history of neurological conditions
- Psychiatric Medication Log
- Somatic Therapies Log
- Clinical Psychiatric Evaluation
- Diagnostic evaluation by investigator
 - Meets DSM-5 criteria for MDD, but does not meet DSM-5 criteria for Bipolar Disorder, Schizophrenia, Schizophreniform disorder, schizoaffective disorder, mental retardation, Pervasive Development Disorder
 - o No psychotic features during the current depressive episode
 - Verify current depressive episode has lasted at least 4 weeks
 - Verify that patient has had at least two adequate trials of antidepressant therapy
- Urine pregnancy test for females of child bearing potential
- Diagnostic Interview
 - o MINI 7.0.2
- Clinician Rated Scales
 - MADRS
 - o YMRS
- Cognitive Assessments
 - MoCA

If patients meet eligibility criteria, they will be randomized into either the ECT or ketamine arm via a secure electronic data management system. Randomization can be done by study staff after the screening visit. Depending on which arm the patient is randomized to, the study nurse will schedule them for their Baseline/Visit 1 according to the site's clinical or research schedule.

7.1.1 Screen Failures

If the patient fails to qualify for the study after signing the informed consent form, they will be considered a screen failure. Patients who screen fail and are not randomized will be eligible to rescreen at a later date. Patients should only be enrolled into the study once, therefore patients who have been randomized will not be eligible for future screening.

7.2 Baseline /Visit 1 (Randomization to occur as soon as possible, but within 1 week after eligibility is confirmed)

- Update Medical History
- Update Psychiatric Medication Log
- Update Somatic Therapies Log
- Clinical Psychiatric Evaluation
- Vitals (BP, heart rate, height, weight)
- Evaluation for AEs and SAEs

Questionnaires to be Completed Prior to Treatment

- Patient Rated Behavioral Scales
 - QIDS-SR-16 (to be completed first)
 - o SMCQ
 - o PGI-S
 - o QOLS
 - PRISE
 - o CPFQ
- Clinician Rate Behavioral Scales
 - MADRS
 - o CSSRS
 - YMRS
 - o CGI-S
- Cognitive Assessments
 - COWAT
 - HVLT-R
 - Stroop
 - NAART

ECT Procedure or Ketamine Infusion

Questionnaires to be Completed Post Treatment*

- CADSS
- o BPRS

7.3 Treatment Visits (To occur over 3 to 5 weeks)

7.3.1 ECT Arm

Prior to each treatment, patients will be assessed if clinically appropriate for the treatment. Components of the evaluation for ECT will vary on a case-by-case basis. Each site will perform the following minimal set of assessments:

- Update Medical History
- Update Psychiatric Medication Log
- Update somatic therapies log
- Vitals (BP, heart rate, weight)
- Evaluation for Adverse Events or Serious Adverse Events
- Clinical Psychiatric Evaluation
- Patient and Clinician Rated Behavioral Scales (to be completed at Baseline/Visit 1, Visit 2, Visit 4, Visit 6, Visit 7, and Visit 9)

Prior to Treatment:

- Patient Rated Behavioral Scales
 - QIDS-SR-16 (To be completed first)
 - GSE-MY (Not completed at Baseline/Visit 1)
 - o SMCQ
 - o PGI-S & PGI-I (PGI-I not completed at Baseline/Visit 1)
 - o QOLS
 - o PRISE
 - o CPFQ
- Clinician Rated Behavioral Scales
 - o MADRS
 - o CSSRS
 - YMRS
 - CGI-S & CGI-I (CGI-I not completed at Baseline/Visit 1)
- Post Treatment (clinician rated)
 - o CADSS
 - o BPRS

^{*}Patients in the ECT arm will need to have a recovery period prior to completing the post treatment questionnaires.

7.3.2 Ketamine Arm

Prior to each treatment, patients will be assessed if clinically appropriate for the treatment. Each site will follow their standard of care for evaluating patients for ketamine treatment. Each site will perform the following minimal set of assessments:

- Update Medical History
- Update Psychiatric Medication Log
- Update Somatic Therapies Log
- Vitals (BP, heart rate, weight)
- Evaluation for Adverse Events or Serious Adverse Events
- Clinical Psychiatric Evaluation
- Patient and Clinician Rated Behavioral Scales (to be completed at every visit)

Prior to Treatment:

- Patient Rated Behavioral Scales (to be completed at every visit)
 - QIDS-SR-16 (To be completed first)
 - GSE-MY (Not completed at Baseline/Visit 1)
 - o SMCQ
 - o PGI-S & PGI-I (PGI-I not completed at Baseline/Visit 1)
 - o QOLS
 - o PRISE
 - o CPFQ
- Clinician Rated Behavioral Scales (to be completed at every visit)
 - o MADRS
 - o CSSRS
 - o YMRS
 - CGI-S & CGI-I (CGI-I not completed at Baseline/Visit 1)

Post Treatment (clinician rated):

- CADSS
- o BPRS

7.3.3 Completion and/or Early Termination of Treatment Phase

Investigators can end the treatment phase early, before the maximum number of treatments are completed, if:

- The clinician feels the patient has achieved a sustained remission (QIDS-SR-16 score <5 on two consecutive assessments) or the clinician determines additional treatments are not clinically warranted
- The patient has worsening depression, severe psychotic symptoms, or becomes suicidal

If these situations occur the patient should be scheduled for an End of Treatment Visit. The patient can decide not to continue treatment for any reason. They should be encouraged to complete an End of Treatment Visit.

Confidential Page **22** of **40** Protocol V7.0 16Feb2022

7.4 End of Treatment (EOT) Visit

Patients should complete an EOT visit within three (3) days of their last study treatment. If patients do not stop treatment early, this will occur after the 9th ECT treatment or the 6th ketamine treatment. If patients stop earlier, the EOT visit should occur within three (3) days of this final treatment. Patients may continue to receive ECT or ketamine clinically, but the EOT visit marks the end of the acute treatment phase for the study.

- Vitals (BP, Heart rate)
- Update Medical History
- Update Psychiatric Medication Log
- Update Somatic Therapies Log
- Evaluation for AEs or SAEs
- Clinical Psychiatric Evaluation
- Patient Rated Behavioral Scales
 - QIDS-SR-16 (to be completed first)
 - o GSE-MY
 - o SMCQ
 - o PGI-S & PGI-I
 - o QOLS
 - o PRISE
 - o CPFQ
 - Treatment Preference Questionnaire
- Clinician Rated Behavioral Scales
 - MADRS
 - o CSSRS
 - o YMRS
 - o BPRS
 - o CGI-S & CGI-I
 - CADSS
- Cognitive Assessments
 - o MoCA
 - o COWAT
 - o HVLT-R
 - Stroop

Patients will be classified as responders or non-responders after the EOT Visit.

Responders will be patients who had a \geq 50% decrease in their QIDS-SR-16 score from Baseline/Visit 1 to the EOT Visit. Responders will be asked to participate in the follow-up

phase of the study. Follow-up visits may occur one month, three months, and six months after the EOT Visit, depending on the date of enrollment relative to the end of study.

Non-responders will have had < 50% decrease in their QIDS-SR-16 score from Baseline/Visit 1 to the EOT Visit. Non-responders will not be seen for follow-up visits. However, these patients will receive a follow-up phone call one month after the End of Treatment Visit.

Inpatient / Outpatient Status - If the patient was an inpatient at randomization, record if they were discharged during treatment and the date of discharge, at the End of Treatment Visit.

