Patient	within one w
Participation	
and Duration of	After patient
the Study	therapy. Pati
	weeks (+ two
	over three w

The screening period will be a maximum of 28 days. Randomization should occur within one week after eligibility is confirmed.

After patients are enrolled they will be randomized to either ECT or ketamine therapy. Patients in the ECT arm will receive up to nine treatments over three weeks (+ two weeks). Patients in the ketamine arm will receive up to six treatments over three weeks (+ two weeks).

Patients in both arms classified as responders may have three additional visits, at Month 1, Month 3, and Month 6 after the End of Treatment visit, depending on the date of enrollment relative to the end of study.

Patients in both arms classified as Non-responders will receive a phone call one month after the End of Treatment visit.

Key Selection Criteria

INCLUSION CRITERIA

- Written informed consent before any study related procedures are performed
- 2. Inpatients or outpatients referred by their providers for ECT treatment and eligible for ECT treatment
- 3. Males/females at least 21 years of age but no older than 75 years of age
- 4. Meet DSM-5 criteria for a Major Depressive Episode as determined by both:
 - A. a clinician's diagnostic evaluation and
 - B. confirmed with the MINI International Neuropsychiatric Interview (MINI 7.0.2)
- 5. A current depressive episode that has lasted a minimum of 4 weeks
- 6. Meet all of the following criteria on symptom rating scales at screening:
 - A. Montgomery Asberg Depression Rating Scale (MADRS) score >20
 - B. Young Mania Rating Scale (YMRS) of ≤ 5
 - C. Montreal Cognitive Assessment (MoCA) of ≥18
- 7. Have had ≥ 2 adequate trials of antidepressants or augmentation strategies during their lifetime. An adequate trial is defined as 4 weeks of medication at the minimum FDA approved dose. This will be equal to a trial rating of 3 or more.
- 8. In the opinion of the investigator, the patient is willing and able to comply with scheduled visits, treatment plan, and other trial procedures for the duration of the study

EXCLUSION CRITERIA

- Meet DSM-5 criteria for bipolar disorder, schizophrenia, schizophreniform disorder, schizoaffective disorder, mental retardation, or pervasive developmental disorder
- Meets any exclusion criteria for ECT or ketamine treatment as described in the clinical guidelines or according to investigator judgment
- 3. The patient is pregnant or breast feeding

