All patients will complete self-reported cognitive assessments, depression questionnaires, and quality of life scales at the Baseline Visit/Visit 1 and throughout the acute treatment phase of the study (see Schedule of Events). Diagnostic interviews and clinician rated scales will also be performed at regular intervals throughout the acute treatment phase.

After the acute treatment phase, all patients will complete an EOT visit within 3 days of their last study treatment and will be classified as either a responder or a nonresponder. Patients may continue to receive ECT or ketamine clinically after the EOT visit, but this will mark the end of the acute treatment phase of the study. If the patient is a responder, any ECT or ketamine treatments administered after the EOT visit will be recorded in the follow-up phase. If the patient is not a responder they will receive a phone call one month after the End of Treatment Visit for completion of PGI-I, PGI-S, QIDS and MADRS, and record any ECT or ketamine treatments administered after the EOT visit. This will conclude their participation in the study and they will be

Confidential Page **13** of **40** Protocol V7.0 16Feb2022 treated clinically.

Responder: a patient who achieves a \geq 50% decrease in their QIDS-SR-16 score from Baseline/Visit 1 to the End of Treatment visits. Responders may continue in the study for three follow-up visits at one month, three months, and six months after the EOT Visit, depending on the date of enrollment relative to the end of study. They will continue naturalistic treatment with a clinician of their choice.

Non-Responder: a patient who achieves <50% decrease in their QIDS-SR-16 score from Baseline/Visit 1 to the End of Treatment Visit. Non-responders will receive a phone call at one month after the EOT Visit. They will be exited from the study after the one month phone follow-up visit and will not be contacted or seen for the three and six month follow-up visits. They will continue treatment with the clinician of their choice.

Early Completion of Acute Treatment Phase

The investigator or patient can choose to stop treatment at any time. Investigators will monitor patients closely for signs of improvement, remission, or decline. The investigator will use his or her discretion and clinical judgment to determine if a patient should stop treatment and be scheduled for an End of Treatment Visit.

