7.8 Lost to Follow-Up

Contact information from the patient, including an emergency contact will be obtained at the time of screening. This information will be reviewed and verified at each clinic visit and telephone contact.

Patients will be considered lost to follow-up (LTFU) after the End of Treatment phase, when one of the following is met:

- For Non-Responders in the one month Follow-Up Phase patients will be considered LTFU after 3 attempts to contact the patient.
- For Responders in the Follow-Up Phase patients will be considered LTFU only after the Month 6 Visit, or at the end of study, whichever comes first.

For each missed visit, study staff should make three attempts to contact the patient as soon as possible at various intervals. The site should access medical records, other health care professionals, institutional databases and any other means to contact the patient as allowed by their IRB. All attempts to contact the patient should be documented in the research chart and medical records.

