8.3 Serious Adverse Events

All SAEs that meet the following definition will be collected from the time of consent until completion of either the One Month Follow-Up Call (for non-responders) or throughout the applicable follow-up visit (for responders).

- Results in death
- Is immediately life-threatening
- Requires in-patient hospitalization or prolongation of existing hospitalization
- Results in persistent or significant disability/incapacity or substantial disruption of the ability to conduct normal life functions
- Is a congenital abnormality or birth defect
- Is an important medical event that may jeopardize the patient or may require medical intervention to prevent one of the outcomes listed above

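### A consenting patient with no End of Treatment QIDS-SR-16 has no clearly assigned Month 1 contact and no defined end to SAE collection

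*Protocol*

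**What the plan says.** Protocol 7.4 sets up two groups: "Patients will be classified as responders or non-responders after the EOT Visit". Protocol 6.2.2 defines the second: "Patients who have less than a 50% decrease in QIDS-SR-16 score from the Baseline/Visit 1 to the EOT Visit will be classified as non-responders". The responder definition (sections 3, 6.2.1 and 7.4) mirrors it with a fall of at least 50% over the same interval. No section says how to classify a patient whose EOT score is missing.

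Section 3 assumes that the case will not arise, since everyone is expected to attend and to be given one of the two labels: "all patients will complete an EOT visit within 3 days of their last study treatment and will be classified as either". Section 7.3.3 is weaker for patients who choose to stop: "They should be encouraged to complete an End of Treatment Visit". Section 7.7 asks the investigator to request an EOT visit from anyone who discontinues treatment or participation. The SAP (Analysis of primary endpoint) plans sensitivity analyses that impute missing primary endpoints.

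What follows EOT is written by class:

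- **Month 1 call.** Synopsis: "Patients in both arms classified as Non-responders will receive a phone call one month after the End of Treatment visit". Section 7.5.2 and the schedule of events place the call under non-responders. It covers AEs and SAEs, further ECT or ketamine, psychotropic treatment, PGI, QIDS and MADRS.
- **Month 1, 3 and 6 visits.** Responders only (7.5.1).
- **Lost to follow-up.** Section 7.8: "Patients will be considered lost to follow-up (LTFU) after the End of Treatment phase, when one of the following is met". One rule for non-responders and one for responders follow.
- **SAE window.** Section 8.3 collects SAEs from consent "until completion of either the One Month Follow-Up Call (for non-responders) or throughout the applicable follow-up visit (for responders".

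**The concern.** Because both labels need an EOT score, a patient without one fits neither definition, and the steps that depend on the label do not say what to do. Sites may handle such patients differently, and in an open-label trial the handling could also differ by arm.

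Safety ascertainment is the main issue. Without a scheduled contact, new SAEs after the last attended visit come to light only if a site happens to learn of them, and the observation period behind the SAE percentages is not fixed for this group. A lesser issue is that the telephone QIDS and MADRS, which could reach patients who will not attend in person, are not clearly assigned to the patients whose primary endpoint is missing.

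**Working it through.** **1. Attrition allowances, which bound the group's size.** The SAP (Sample size justification) assumes 50% response on ECT, a true difference of +5 points, a 10-point margin and one-sided alpha of 0.025. It states that 346 patients give 80% power.

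With n per arm, the Farrington-Manning power is Φ[(p_K − p_E + M − 1.96·s0)/s1]. Here s1 = √{[p_K(1−p_K) + p_E(1−p_E)]/n}, and s0 has the same form at the rates fitted under a difference of −M.

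- n = 173, p_K = 0.55, p_E = 0.50, M = 0.10.
- Fitted null rates 0.474 and 0.574, so s0 = 0.0534 and s1 = 0.0536.
- (0.15 − 1.96 × 0.0534)/0.0536 ≈ 0.844, giving 80.1% power. The stated 346 is reproduced.
- SAP attrition of 15%: 346/0.85 = 407.06, or 408 rounded up to equal arms, against the stated 400. Conversely, 400 × 0.85 = 340, with power 79.4%.
- Protocol section 9: 81.8% power at +10 points with a 5-point margin is reproduced at 400 × 0.90 = 360 patients (81.8%), not at 400 (85.6%). The 10% attrition is therefore already inside that figure.

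**2. Upper bound on patients affected.**

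| Source | Arithmetic | Patients |
|---|---|---|
| Protocol, 10% | 400 × 0.10 | 40 |
| SAP, 346 evaluable out of 400 | 400 − 346 | 54 |
| SAP, 15% | 400 × 0.15 | 60 |

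This treats every lost patient as lacking an EOT QIDS and still open to contact. Neither document defines attrition that way. If half fitted that description, the range would be 20 to 30; the half is an assumption.

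**3. What each provision gives a consenting patient with no EOT score.**

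| Provision | What it gives |
|---|---|
| 6.2.1, 6.2.2, 7.4 (classification) | No label; both need the EOT score |
| Section 3, design text | Gives the call to a patient who is not a responder, but times it from EOT and then defines non-responder by the EOT score |
| 7.5.2, schedule of events | Call listed for non-responders only |
| 7.7 Withdrawal | EOT requested; unresolved AEs followed; no later QIDS, MADRS or search for new events |
| 7.8 Lost to follow-up | Three attempts per missed visit, plus use of records and other contacts; no assessment assigned if reached; loss defined only by class |
| 8.3 SAEs | Collection starts at consent; both end points depend on class |
| 7.5.3 End of study | Completion is by class; consent withdrawal, loss to follow-up, death and clinician discretion are not |

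A randomised but untreated patient is a further case: EOT is timed from the last study treatment, and there is none.

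**4. Would a Month 1 call change the extreme-case analysis?** Take observed response of 55% on ketamine and 50% on ECT, 200 per arm and 15% missing in each arm (30 missing, 170 observed). Worst-best: ketamine 0.55 × 170/200 = 46.75%; ECT (0.50 × 170 + 30)/200 = 57.5%; difference −10.75 points. After a Month 1 call the EOT outcome is still missing for the same 30 per arm, so the bound is still −10.75. The call leaves these bounds where they were.

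**The case against.** The strongest counter-argument is that the protocol already covers these patients. Section 3 gives the call to a patient who is not a responder, and someone with no EOT score has not shown a 50% fall. Section 7.7 requests an EOT visit and follows unresolved AEs. Section 7.8 requires three attempts for each missed visit, which includes a missed EOT, and use of records and other providers. Patients whom the investigator stops for worsening or suicidality are to be scheduled for EOT; the weaker wording applies to those who choose to stop.

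Much of this stands, and it rules out three stronger readings that a reader might infer.

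- **That SAE collection stops for these patients.** Nothing ends it. Its end is undefined, and no contact is scheduled to find new events.
- **That the missing-data analyses lose their best evidence.** QIDS and MADRS are collected throughout the acute phase in both arms. Scores near dropout are closer to the EOT endpoint than a call a month later, which may reflect further treatment.
- **That the defect is worth 5 to 15 points on the treatment difference.** That shift comes from missing EOT outcomes, which the call does not supply.

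Nor do the documents show that patients who drop out are the likeliest to have worsened.

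The counter-argument does not close the gap. Section 3 goes on to define non-responder by the EOT score and times the call from a visit that did not take place. Sections 7.7 and 7.8 assign no Month 1 assessment and no end to SAE collection.

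**Conclusion.** The concern holds as a gap in routing and safety follow-up. A patient without an EOT QIDS-SR-16 who has not withdrawn consent for contact has no clearly assigned Month 1 safety, QIDS or MADRS contact, and the SAE window has no stated end for that patient. The text is ambiguous and does not forbid a call.

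The size is at most about 40 to 60 of 400 patients. This rests on all of the 10% to 15% attrition being a missing EOT score. The documents do not give the true number, and patients who withdraw consent for future information fall outside the point, because section 7.7 bars further data collection from them. The gap does not affect sample size, alpha, power or the principal analysis. It is worth correcting because the remedy is cheap and makes SAE ascertainment uniform.

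**What to change.** In Protocol 6.2.2, 7.5.2, 7.8 and 8.3, state that any randomised patient without an EOT QIDS-SR-16 who has not withdrawn consent for contact:

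- receives the existing Month 1 call with its present content, timed from the last study treatment, or from randomisation if untreated;
- is lost to follow-up after three failed attempts at that call;
- has SAEs collected up to that call.

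Say that this is routing only and does not make the patient a non-responder for the primary endpoint. Bring the section 3 wording into line.

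In the SAP, add the acute-phase QIDS-SR-16 and MADRS scores already collected to the imputation model, which now names only baseline variables and EOT changes. Month 1 scores can be optional further auxiliaries.

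The cost is a short amendment and a few dozen calls on an existing form. Some calls will go unanswered, and some Month 1 scores will reflect later treatment. If follow-up has already closed (SAP version 2.0 was drafted at the end of the study), report by arm how many patients lacked an EOT score and how long their SAEs were followed.
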